Appendix A Efficacy analysis SAS pseudo code

Primary Analysis missing data imputation:

1. Multiple imputations in participants who prematurely discontinued the study treatment before the Week-30 visit:

```
proc mi data= data_IN out= data_OUT_DISC n impute=10000 seed=14822;  
    where PEOTF30L = "Y";  
    by ARM;  
    var BASE AVAL_W30;  
    monotone regression (AVAL_W30= BASE );  
run;
```

2. Multiple imputations in participants who stay on the study treatment until the Week-30 visit

```
proc mi data= data_IN out= data_OUT_COMPL_MI n impute=10000 seed=14822;  
    where PEOT30FL='N' and (ARM='Placebo' or (ARM ne 'Placebo' and AVAL_W30 =. ));  
    class HbA1c strata BMI strata;  
    var HbA1c strata BMI strata base AVAL_W30;  
    monotone regression (AVAL_W30 = HbA1c strata BMI strata BASE );  
run;
```

3. Transform dataset of EFPEG participants who are under treatment at Week 30 visit with a collected endpoint to have 10 000 replications.

```
Data data_OUT_COMPL_EFPEG;  
Set data_IN (where=( PEOT30FL='N' and ARM ne 'Placebo' and AVAL_W30 ne .));  
n_imput=1;  
%do i = 1 %to 10 000;  
n_imput=n_imput+1;  
%end;  
run;
```

4. Combine multiple imputations from the three subsets of participants

```
Data  dataMI;  
set   data_OUT_DISC  
      data_OUT_COMPL_MI  
      data_OUT_COMPL_EFPEG;  
run;
```

Back-up plan:

```
Data  data_OUT_COMPL_EFPEG;  
Set   data_IN (where=( ARM ne 'Placebo' and AVAL_W30 ne .);  
n_imput=1;  
%do i = 1 %to 10 000;  
n_imput=n_imput+1;  
%end;  
run;  
  
proc mi data =data_IN out=data_OUT_MI nimpute=10000 seed=14822;  
  where ARM='Placebo' or (ARM ne 'Placebo' and AVAL_W30 =.);  
  class HbA1c_strata BMI_strata;  
  var HbA1c_strata BMI_strata base AVAL_W30;  
  monotone regression (AVAL_W30 = HbA1c_strata BMI_strata BASE );  
run;  
data  dataMI;  
set   data_OUT_MI  
      data_OUT_COMPL_EFPEG;  
run;
```

Sensitivity analysis (*If more than 10 missing endpoint data impacted by COVID-19*):

```
#3 DATA data_OUT_COMPL;  
      Set data_IN (where = (PEOTF56L='N' and W56_missing = "N"));  
      _imputation_=0;  
      do i = 1 to 10 000;  
      _imputation_=imputation_+1;  
      output;  
      end;  
run;
```

#1 Multiple imputations in participants who prematurely discontinued the study treatment before the Week 56 visit:

```
proc mi data= data_IN out=data_OUT_DISC nimpute=10000 seed=14822;  
      where PEOTF56L = "Y";  
      by ARM;  
      var BASE AVAL_W56;  
      monotone regression (AVAL_W56= BASE );  
run;
```

```
#2a proc mi data      =data_IN out=data_OUT_MI nimpute=10000 seed=14822;  
      where PEOT56FL='N' and ((ARM='Placebo' and W56_missing = "N") or (ARM = 'Placebo' and W56_missing = "Y" and  
COVID = "N") or (ARM ne 'Placebo' and W56_missing = "Y" and COVID = "N"));  
      class HbA1c_strata BMI_strata;  
      var HbA1c_strata BMI_strata base AVAL_W56;  
      monotone regression (AVAL_W56 = HbA1c_strata BMI_strata BASE);  
run;
```

```
data data_OUT_MI_MISSING;
  set data_OUT_MI;
  if W56_missing = "Y";
run;

proc sort data= data_IN out=data_IN_COVID;
  by ARM;
run;

#2b step 1
proc mi data  =data_IN_COVID out= monotone nimpute=10000 seed=14822;
  by ARM;
  where PEOT56FL='N' and (W56_missing ne "Y" or (W56_missing = "Y" and COVID="Y"));
  mcmc chain=multiple impute=monotone
  var BASE AVAL_W12 AVAL_W30 AVAL_W43 AVAL_W56;
  /* For body weight, include Weeks 4, 8, 12, 24, 30, 43, and 56 */
run;

#2b step2
proc mi data= monotone out= OUT_MI_MISSING_COVID nimpute=1 seed=14822;
  by ARM _imputation_;
  class HbA1c_strata BMI_strata;
  monotone reg ( / details);
  var HbA1c_strata BMI_strata BASE AVAL_W12 AVAL_W30 AVAL_W43 AVAL_W56;
  /* For body weight, include Weeks 4, 8, 12, 24, 30, 43, and 56 */
run;
```

```
data data_OUT_MI_MISSING_COVID;  
  set OUT_MI_MISSING_COVID;  
  if W56_missing = "Y";  
run;
```

```
data  dataMI;  
set   data_OUT_DISC  
      data_OUT_MI_MISSING  
      data_OUT_MI_MISSING_COVID  
      data_OUT_COMPL;  
run;
```

In this sample SAS® (version 9.4) code:

- DATA_IN is the input dataset including one observation per participant in the ITT population with Baseline HbA1c value and change from baseline at Week 30.
- data_OUT_DISC is the output dataset including observed and imputed data for participants who have prematurely discontinued the treatment.
- data_OUT_COMPL_MI is the output dataset including observed and imputed data for all Placebo participants who have completed the 30-week study treatment period and all Efpeg participants who have completed the 30-week study treatment period without Week 30 endpoint.
- Data_OUT_COMPL_EFPEG is the output dataset included observed data for Efpeg participants who have completed the 30-week study treatment period and have Week 30 endpoint.
- DataMI is the final output containing 10,000 lines by participant with all observed and imputed data used for the ANCOVA.
- PEOT30/56FL is the variable indicating whether the participant prematurely discontinued the study treatment (PEOT30/56FL="Y" if the participants prematurely discontinued the study treatment before Week 30/56 visit and PEOT30/56FL="N" if the participant stay on the study treatment until Week 30/56 visit).
- ARM is the randomized treatment group (Placebo, Efpeglenatide 2mg, Efpeglenatide 4mg, Efpeglenatide 6mg).

- HbA1c_strata is the randomization stratum of screening Hb1Ac (<8%, \geq 8%)
- BMI_strata is the randomization stratum of BMI at Visit 3(<30, \geq 30)
- BASE is the baseline HbA1c.
- AVAL_W30/56 is the change from baseline in HbA1c at Week 30/56.
- W56_missing = “Y” if the Week 56 value is missing, otherwise W56_missing = “N”.
- COVID = “Y” if the missing data is impacted by COVID-19, otherwise COVID = “N”.
- The seed (14822) has been chosen arbitrarily and is based on the study code (EFC14822).

Appendix B Criteria for potentially significant abnormalities - for Phase 2/3 studies (oncology excepted)

Parameter	PCSA	Comments
Clinical Chemistry		
ALT	By distribution analysis: >3 ULN >5 ULN >10 ULN >20 ULN	Enzymes activities must be expressed in ULN, not in IU/L. Concept paper on DILI – FDA draft Guidance Oct 2007. Internal DILI WG Oct 2008. Categories are cumulative. First row is mandatory. Rows following one mentioning zero can be deleted.
AST	By distribution analysis: >3 ULN >5 ULN >10 ULN >20 ULN	Enzymes activities must be expressed in ULN, not in IU/L. Concept paper on DILI – FDA draft Guidance Oct 2007. Internal DILI WG Oct 2008. Categories are cumulative. First row is mandatory. Rows following one mentioning zero can be deleted.
Alkaline Phosphatase	>1.5 ULN	Enzymes activities must be expressed in ULN, not in IU/L. Concept paper on DILI – FDA draft Guidance Oct 2007. Internal DILI WG Oct 2008.
Total Bilirubin	>1.5 ULN >2 ULN	Must be expressed in ULN, not in μ mol/L or mg/L. Categories are cumulative. Concept paper on DILI – FDA draft Guidance Oct 2007. Internal DILI WG Oct 2008.
Conjugated Bilirubin	>35% Total Bilirubin and TBILI >1.5 ULN	Conjugated bilirubin dosed on a case-by-case basis.
ALT and Total Bilirubin	ALT >3 ULN and TBILI >2 ULN	Concept paper on DILI – FDA draft Guidance Oct 2007. Internal DILI WG Oct 2008. To be counted within a same treatment phase, whatever the interval between measurement.

[figure not shown]
Parameter	PCSA	Comments
CPK	>3 ULN >10 ULN	FDA Feb 2005. Am J Cardiol April 2006. Categories are cumulative. First row is mandatory. Rows following one mentioning zero can be deleted.
CLcr (mL/min) (Estimated creatinine clearance based on the Cokcroft-Gault equation)	<15 (end stage renal disease) ≥15 - <30 (severe decrease in GFR) ≥30 - < 60 (moderate decrease in GFR) ≥60 - <90 (mild decrease in GFR) ≥ 90 (normal GFR)	FDA draft Guidance 2010 Pharmacokinetics in patients with impaired renal function-study design, data analysis, and impact on dosing and labeling
eGFR (mL/min/1.73m2) (Estimate of GFR based on an MDRD equation)	<15 (end stage renal disease) ≥15 - <30 (severe decrease in GFR) ≥30 - < 60 (moderate decrease in GFR) ≥60 - <90 (mild decrease in GFR) ≥ 90 (normal GFR)	FDA draft Guidance 2010 Pharmacokinetics in patients with impaired renal function-study design, data analysis, and impact on dosing and labeling
Creatinine	≥150 µmol/L (Adults) ≥30% change from baseline ≥100% change from baseline	Benichou C., 1994.
Uric Acid		Harrison- Principles of internal Medicine 17 th Ed., 2008.
Hyperuricemia	>408 µmol/L	
Hypouricemia	<120 µmol/L	
Blood Urea Nitrogen	≥17 mmol/L	
Chloride	<80 mmol/L ≥115 mmol/L	
Sodium	≤129 mmol/L ≥160 mmol/L	
Potassium	<3 mmol/L ≥5.5 mmol/L	FDA Feb 2005.
Total Cholesterol	≥7.74 mmol/L	Threshold for therapeutic intervention.
Triglycerides	≥4.6 mmol/L	Threshold for therapeutic intervention.
Lipasemia	≥3 ULN	
Amylasemia	≥3 ULN	
Glucose		
Hypoglycaemia	≤3.9 mmol/L and <LLN	ADA May 2005.
Hyperglycaemia	≥11.1 mmol/L (unfasted); ≥7 mmol/L (fasted)	ADA Jan 2008.

Parameter	PCSA	Comments
HbA1c	>8%	
Albumin	≤25 g/L	
CRP	>2 ULN or >10 mg/L (if ULN not provided)	FDA Sept 2005.
Hematology		
WBC	<3.0 Giga/L (Non-Black); <2.0 Giga/L (Black) ≥16.0 Giga/L	Increase in WBC: not relevant. To be interpreted only if no differential count available.
Lymphocytes	>4.0 Giga/L	
Neutrophils	<1.5 Giga/L (Non-Black); <1.0 Giga/L (Black)	International Consensus meeting on drug-induced blood cytopenias, 1991. FDA criteria.
Monocytes	>0.7 Giga/L	
Basophils	>0.1 Giga/L	
Eosinophils	>0.5 Giga/L or >ULN (if ULN ≥0.5 Giga/L)	Harrison- Principles of internal Medicine 17 th Ed., 2008.
Hemoglobin	≤115 g/L (Male); ≤95 g/L (Female) ≥185 g/L (Male); ≥165 g/L (Female) Decrease from Baseline ≥20 g/L	Criteria based upon decrease from baseline are more relevant than based on absolute value. Other categories for decrease from baseline can be used (≥30 g/L, ≥40 g/L, ≥50 g/L).
Hematocrit	≤0.37 v/v (Male); ≤0.32 v/v (Female) ≥0.55 v/v (Male); ≥0.5 v/v (Female)	
RBC	≥6 Tera/L	Unless specifically required for particular drug development, the analysis is redundant with that of Hb. Otherwise, consider FDA criteria.
Platelets	<100 Giga/L ≥700 Giga/L	International Consensus meeting on drug-induced blood cytopenias, 1991.
Urinalysis		
pH	≤4.6 ≥8	
Vital signs		
HR	≤50 bpm and decrease from baseline ≥20 bpm ≥120 bpm and increase from baseline ≥20 bpm	To be applied for all positions (including missing) except STANDING.

Parameter	PCSA	Comments
SBP	≤ 95 mmHg and decrease from baseline ≥ 20 mmHg ≥ 160 mmHg and increase from baseline ≥ 20 mmHg	To be applied for all positions (including missing) except STANDING.
DBP	≤ 45 mmHg and decrease from baseline ≥ 10 mmHg ≥ 110 mmHg and increase from baseline ≥ 10 mmHg	To be applied for all positions (including missing) except STANDING.
Orthostatic Hypotension		
Orthostatic SDB	≤ -20 mmHg	
Orthostatic DBP	≤ -10 mmHg	
Weight	$\geq 5\%$ increase from baseline $\geq 5\%$ decrease from baseline	FDA Feb 2007.
ECG		Ref.: ICH E14 guidance (2005) and E14 Q&A (2012), and Cardiac Safety Research Consortium White Paper on PR and QRS (Nada et al. Am Heart J. 2013; 165(4): 489-500)
HR	<50 bpm <50 bpm and decrease from baseline ≥ 20 bpm <40 bpm <40 bpm and decrease from baseline ≥ 20 bpm <30 bpm <30 bpm and decrease from baseline ≥ 20 bpm >90 bpm >90 bpm and increase from baseline ≥ 20 bpm >100 bpm >100 bpm and increase from baseline ≥ 20 bpm >120 bpm >120 bpm and increase from baseline ≥ 20 bpm	Categories are cumulative

Parameter	PCSA	Comments
PR	
>200 ms
 
>200 ms and increase from baseline ≥25%
 
> 220 ms
 
>220 ms and increase from baseline ≥25%
 
> 240 ms
 
> 240 ms and increase from baseline ≥25%
	Categories are cumulative
QRS	
>110 ms
 
>110 msec and increase from baseline ≥25%
 
>120 ms
 
>120 ms and increase from baseline ≥25%
	Categories are cumulative
QT	>500 ms	
QTc	
Absolute values (ms)
 
>450 ms
 
>480 ms
 
>500 ms
 
Increase from baseline
 
Increase from baseline]30-60] ms
 
Increase from baseline >60 ms
	
To be applied to any kind of QT correction formula.
 
Absolute values categories are cumulative
 
QTc >480 ms and QTc>60 ms are the 2 PCSA categories to be identified in individual subjects/patients listings.

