#### 9.4.1 Efficacy analyses

**Table 5 - Efficacy analyses**

Endpoint	Statistical Analysis Methods
Primary Change in HbA1c from Baseline to Week 30	
Primary analysis:
 
The primary efficacy endpoint will be analyzed using all HbA1c values at Baseline and Week 30 (observed or imputed), regardless of treatment discontinuation or initiation of rescue therapy (ITT estimand).
 
The primary analysis method for the primary efficacy endpoint will be an ANCOVA model with missing values imputed by MI analysis method in two parts as follows:
 

Missing endpoint data in participants who prematurely discontinue the study treatment before the Week 30 visit will be imputed using a model estimated from participants in the same treatment arm who prematurely discontinue the study treatment before the Week 30 visit but have the measurement for the endpoint (retrieved dropouts). Considering that the number of participants in each treatment arm who discontinue the study treatment but have the measurement for the endpoint is expected to be small, a simple imputation model will be used, where only the baseline measurements are included as the predictor. Each treatment group will have their own imputation model. Missing data will be imputed using the regression method.

Missing endpoint data in all participants, including those in the efpeglenatide arms, who stay on the study treatment until the Week 30 visit will be imputed separately, using a model estimated from participants in the placebo group who stay on the study treatment until the Week 30 visit and have the endpoint data available. The imputation model will include the randomization strata and corresponding baseline values without including any intermediate. Missing data will be imputed using the regression method.

 
In this analysis, missing endpoint values will be imputed 10 000 times to generate 10 000 data sets with complete data. The completed data sets will be analyzed using an ANCOVA model with treatment groups, randomization strata, and geographical regions as fixed effects and the corresponding baseline values as a covariate.
 
The Baseline value is defined as the last available value prior to the first dose administration of IMP or the last available value on or before the date of Randomization if not treated with the double-blinded IMP.
 
The results from the 10 000 analyses will be combined using Rubin's formula and provide the adjusted mean change in HbA1c from Baseline to Week 30 (regardless of treatment discontinuation or initiation of rescue therapy) for each treatment group, as well as the difference between each efpeglenatide dose and placebo and the 95% CI for the difference.
 
A hierarchical procedure will be applied to adjust for the multiplicity of comparison on the primary endpoint:
 

First, the highest dose of efpeglenatide (6 mg) will be compared to placebo to demonstrate superiority of this dose versus placebo

If superiority is demonstrated for efpeglenatide 6 mg, the superiority of 4 mg dose of efpeglenatide versus placebo will be tested

If superiority is also demonstrated for 4 mg dose, the lowest dose (2 mg) will be tested for superiority over placebo

 
When the superiority is not obtained in a step, the sequential testing procedure will be stopped.
 
As noted, the number of retrieved dropouts is expected to be small, and may not have sufficient data to support the imputation approach in item 1 described above. If there are less than 5 participants in any arms who prematurely discontinue the study treatment before the Week 30 visit but have the measurement for the endpoint, a back-up imputation method for the primary efficacy analysis will be used. In particular, missing endpoint data in all participants in both

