2.4.4.1 Analysis of primary efficacy endpoint

The statistical test will be 2-sided tests at a nominal 5% significance level.

Hypothesis Testing of the Primary Endpoint

For the primary efficacy variable of change from Baseline to Week 30 in HbA1c (%), the following statistical null hypothesis and alternative will be tested for each efpeglenatide dose:

- H0: No population LS mean treatment difference in reduction in HbA1c from Baseline;
- H1: Efpeglenatide has a higher population LS mean reduction in HbA1c from Baseline than placebo.

Primary Analysis

The statistical analysis for the primary endpoint is described below.

The Baseline value is defined in [Section 2.1.1](#).

The primary analysis will be an analysis of covariance (ANCOVA) modeling with missing values imputed based upon retrieved dropouts in 2 separates parts as follows:

1. Missing endpoint data in participants who prematurely discontinue the study treatment before the Week-30 visit will be imputed using a model built separately in each arm and estimated from participants in the same treatment arm who prematurely discontinue the study treatment before the Week-30 visit but have the measurement for the endpoint (retrieved dropouts). Considering that the number of participants in each treatment arm who discontinue the study treatment but have the measurement for the endpoint is expected to be small, a simple imputation model will be used, where only the Hb1Ac baseline measurements are included as the predictor. Each treatment group will have their own imputation model. Missing data will be imputed using the regression method.
2. Missing endpoint data in all participants, including those in the efpeglenatide arms, who stay on the study treatment until the Week-30 visit will be imputed separately. The washout-imputation method will be used, where missing endpoint data in the efpeglenatide arms, as well as the missing data in the placebo arm, are imputed from a model estimated from participants in the placebo group with endpoint data without including any intermediate values. The imputation model will include the randomization strata and corresponding Hb1Ac baseline values. Missing data will be imputed using the regression method.

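### SAP Appendix A: the primary-analysis replication loop cannot give the 10,000 lines per participant the SAP requires, and SAP 2.4.4.1 and the code name different placebo donors

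*SAP*

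**What the plan says.** **Replication of observed records.** SAP 2.4.4.1 requires 10,000 completed datasets, an ANCOVA on each, and pooling by Rubin's formula, and it refers to Appendix A for the code. Appendix A builds the stacked dataset from three pieces: treatment discontinuers (step 1, PROC MI), on-treatment placebo participants plus on-treatment efpeglenatide participants with a missing value (step 2, PROC MI), and on-treatment efpeglenatide participants with an observed value (step 3, a DATA step). The heading of step 3 states its purpose: "Transform dataset of EFPEG participants who are under treatment at Week 30 visit with a collected endpoint to have 10 000 replications". Its input is selected by "PEOT30FL='N' and ARM ne 'Placebo' and AVAL_W30 ne" missing. The loop body is "n_imput=n_imput+1". The definitions at the end of the appendix give the required result: "DataMI is the final output containing 10,000 lines by participant with all observed and imputed data used for the ANCOVA".

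The Back-up plan repeats the same loop for a wider set: every efpeglenatide participant with an observed Week 30 value, on or off treatment.

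**Placebo donors for on-treatment missing values.** SAP 2.4.4.1 item 2 says that missing values "are imputed from a model estimated from participants in the placebo group with endpoint data without including any intermediate values". Protocol Table 5 (and the synopsis) uses "a model estimated from participants in the placebo group who stay on the study treatment until the Week 30 visit" with endpoint data available.

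**The concern.** Appendix A is where the SAP shows, step by step, how observed and imputed records are joined for the primary test. SAP version 2 removed the non-primary pseudo code and added the Back-up code, so the primary code was kept deliberately. If the join is programmed as printed, apart from syntax repairs, the observed efpeglenatide records do not carry the index of the imputed datasets, and the result contradicts the SAP's own definition of the final dataset.

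The reach goes beyond one endpoint. SAP 2.4.4.2.2 applies the same imputation method to FPG at Week 30, body weight at Weeks 30 and 56, and HbA1c at Week 56. Those account for 10 of the 13 ranked secondary tests (all except the three for HbA1c below 7%). The Back-up plan is a realistic route: it is triggered by fewer than 5 retrieved dropouts in any arm, and both documents expect few.

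The donor wording is a separate matter. A primary estimator should have one definition, and here the SAP text differs from the protocol and from the SAP's own code.

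**Working it through.** **1. The plan's figure.** The requirement is 10,000 lines per participant. With the planned 400 participants that is 400 × 10,000 = 4,000,000 rows, with all 400 present in each imputed dataset.

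**2. What each piece delivers.** PROC MI with 10,000 imputations writes every input record 10,000 times, numbered by `_Imputation_`. Steps 1 and 2 therefore meet the requirement. Step 3 is a DATA step. With no OUTPUT inside the loop, it writes one record per input record, at RUN.

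| Version of the step 3 loop | Rows per participant | `n_imput` | `_Imputation_` |
|---|---|---|---|
| Required | 10,000 | – | 1 to 10,000 |
| As written, loop expands | 1 | 1 + 10,000 = 10,001 | missing |
| As written, loop not honoured, body runs once | 1 | 1 + 1 = 2 | missing |
| OUTPUT added, nothing else changed | 10,000 | 2 to 10,001 | missing |

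The last row shows that OUTPUT alone is not a repair. Grouping by `n_imput` does not help either, because that variable is missing on every PROC MI row. The appendix itself uses the PROC MI index elsewhere: the second step of the COVID-19 imputation runs "by ARM _imputation" (followed by the closing underscore).

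**3. How many participants this concerns.** The documents give no discontinuation or missing rates, so the following is conditional on assumed ones. Let *d* be the proportion stopping treatment before Week 30 and *m* the proportion on treatment with a missing value. The number affected in step 3 is E = 300 × (1 − d − m).

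- d = 5%, m = 0: E = 300 × 0.95 = 285, leaving 400 − 285 = 115 participants with a valid imputation number.
- d = 20%, m = 5%: E = 300 × 0.75 = 225, leaving 400 − 225 = 175.

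The stacked dataset would have (400 − E) × 10,000 + E rows: 1,150,285 and 1,750,225 respectively, against 4,000,000.

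In the Back-up plan, if 5% to 15% of efpeglenatide values are missing, E = 300 × 0.95 = 285 down to 300 × 0.85 = 255. These counts are absences from imputations 1 to 10,000 only if the ANCOVA is run by `_Imputation_`.

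**4. Donor sets side by side.**

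| Source | Donors for on-treatment missing values |
|---|---|
| Protocol synopsis and Table 5 | Placebo, on treatment, endpoint observed |
| Appendix A step 2 (`PEOT30FL='N'`) | Placebo, on treatment, endpoint observed |
| Appendix A, definition of `data_OUT_COMPL_MI` | Placebo participants who completed the 30-week treatment period |
| SAP 2.4.4.1 item 2 | Placebo, endpoint observed |

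The SAP uses the item 2 donor wording again for the Back-up method, where the code does take all placebo participants. Read literally, item 2 is therefore the wider set. Neither SAP change table records a change of donors.

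**The case against.** The strongest reply is that this is labelled pseudo code and sample code, with the right intent stated beside it. The step 3 heading, the definition of the final dataset and the text of 2.4.4.1 all say what is wanted. That stands. Appendix A is not the only specification of the join, the planned method is sound, and a competent programmer could follow the stated intent.

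It also stands that the printed code would probably not run. It has an iterative `%do` in open code, a bound printed with a space, an unclosed parenthesis in the Back-up plan, and a step 1 filter on `PEOTF30L` where the defined flag is `PEOT30FL`. If it did run, the unindexed rows would form an extra group with no placebo participants, which should be noticed. But repairing only the syntax leaves one unindexed row per participant, so the contradiction remains.

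A reader might infer that the primary analysis was, or will be, run on nearly empty efpeglenatide arms and loses its power. The documents do not support this. The ANCOVA and pooling calls are not printed, nothing shows the production program, and any power figure would rest on assumed discontinuation, retrieval and missing rates and on an assumed effect after stopping treatment.

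A reader might also conclude that the COVID-19 block fails in the same way. It does not: it has an OUTPUT statement and names the right index. Its line prints as "imputation_=imputation_+1" after a leading underscore, with none before the right-hand variable, but that underscore may have been lost in PDF reading. Step 2 similarly prints the strata names without the underscores they have in the Back-up plan.

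On donors, item 2 concerns participants who stay on treatment, so the restriction could be read as implied. Its words do not say so.

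**Conclusion.** The point holds as a contradiction between the primary-analysis pseudo code and the SAP's own specification. In step 3 and the Back-up plan each affected efpeglenatide participant gets 1 row instead of 10,000, with no value of `_Imputation_`. Absence from imputations 1 to 10,000 follows if the ANCOVA is run by that index, which is the natural reading because PROC MI writes it, but it is not stated. This is a defect in the code specification and not in the chosen method.

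The donor discrepancy in item 2 is also real. Its effect is probably small, since it only adds placebo participants who stopped treatment but were measured, and both documents expect few of them. It was not quantified.

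**What to change.** - In step 3 and the Back-up plan, replace the loop and `n_imput` with `do _Imputation_=1 to 10000; output; end;`, and close the parenthesis in the Back-up plan.
- Use the defined flags `PEOT30FL` and `PEOT56FL` throughout.
- Sort the stacked dataset by `_Imputation_`. Before the ANCOVA, check that every ITT participant has exactly one row in each of the 10,000 imputations.
- Reword SAP 2.4.4.1 item 2 to name placebo participants still on treatment at Week 30 with endpoint data, as in the protocol and code. Item 2 a) of 2.4.4.2.2 carries the same wording while its code restricts to on-treatment placebo, so edit it in the same way for Week 56.
- In the COVID-19 block, only verify the index line against the source file.

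The cost is SAP and programming wording plus one automated check. Data collection, sample size and the testing order are unaffected.
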